5.5.1. Procedures for Subject Follow-up

Subjects who permanently discontinue randomized treatment will be asked to attend an Early Treatment Discontinuation visit and will be expected to attend in-clinic study visits

through to Follow-up according to the study visit schedule, unless consent is actively withdrawn. Complete details are provided in [Table 7](#) in Section 7.1.

- Early Treatment Discontinuation visit: This visit should occur within 2 weeks of the last dose of randomized treatment.
- Remaining in-clinic visits*:
 - Day 1 through Week 52: Study visits every 12 weeks \pm 2 weeks post Early Treatment Discontinuation visit.
 - Follow-up: Study visit 4 weeks after Week 52.

*Phone visit acceptable in exceptional circumstances.

- In all cases, reasons for Early Treatment Discontinuation and the date of last dose will be recorded.
- If a subject does not agree to continue attending in-clinic or phone visits, other follow-up options to collect study outcomes and vital status should be pursued according to local laws and regulations. If one of these alternate methods to collect study outcomes and vital status is acceptable to the subject, then the subject will be considered to have remained in the study and not to have withdrawn consent.

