9.2. Sample Size Considerations

9.2.1. Sample Size Assumptions

The size of this study has been determined to be sufficient to meet the ICH E1 guideline for subject exposure, number and duration and to provide at least 90% power to test the primary non-inferiority hypothesis with a two-sided 95% CI.

Approximately 300 subjects are planned to be randomized (150 per arm) to receive daprodustat or rhEPO, to provide at least 100 subjects exposed to daprodustat for one year. Subjects will be treated to achieve and maintain Hgb between 10 and 11 g/dL. The expected difference in mean Hgb change from baseline and the EP, between arms, is 0 g/dL and the anticipated between subject standard deviation (SD) is 1.5 g/dL, based on historical rhEPO trials and daprodustat clinical trial experience to date. With a pre-specified non-inferiority margin of -0.75 g/dL, a two-sample T-test and assuming that up to approximately 30% of subjects will permanently stop randomized treatment before Week 28 (start of EP), 300 randomized subjects will provide >90% power to test the primary hypothesis.

With 300 randomized subjects, it is anticipated that the difference in mean Hgb change from baseline between arms will be estimated with a precision of 0.408 g/dL (half width of the two-sided 95% CI) and the largest (most negative) difference between arms that would meet the statistical criterion for non-inferiority would be -0.342 g/dL.

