7.1.2.5. Statistical Analyses/Methods

Primary Hgb Efficacy Statistical Analyses
Endpoint(s)

 • Mean change in Hgb between baseline and EP
Model Specification

 • Hgb during the EP will be defined as the mean of all available post-randomization Hgb values (on and off-treatment) during the EP (Week 28-52). • The ANCOVA model used to quantify the difference in mean Hgb change will adjust for the following baseline values: 
 ○ Treatment ○ Baseline Hgb (see Section 10.5.2) ○ Dialysis type (as randomized, see Section 0) ○ Dialysis start manner (whether dialysis start is planned or unplanned; as randomized)
Multiple Imputation Analysis

 • Multiple imputation analysis will be performed using all available Hgb values (on and off-treatment) and conducted under a set of assumptions about missing Hgb values (see Section 10.6.3). 
 ○ Intermittent missing post-baseline scheduled Hgb data in both arms through Week 52 will be imputed using PROC MI procedure with NIMPUTE = 200 and MCMC IMPUTE = monotone to generate 200 datasets with only monotone missing patterns. Burn in iterations (NBITER) and maximum iteration (MAXITER) will both be set to 500. The seed for reproducibility is set to 201410. The imputations will be done by randomized treatment, dialysis type, and dialysis starting manner. ○ For each of the monotone missing dataset (out of the 200 imputed as indicated above), the missing scheduled Hgb values through Week 52 will be imputed based on the MAR assumption and will be performed using PROC MI by treatment, dialysis type, and dialysis start manner. The monotone regression will have baseline Hgb, prior scheduled (possibly imputed) Hgb values, and may include dialysis type and dialysis start manner, as covariates (see Model Checking & Diagnostics, below). The seed for reproducibility is set to 201410. ○ The low and high cutoffs at Hgb values of 6 g/dL and 15 g/dL will be applied to all imputed Hgb values. ○ EP Hgb values will be computed and compared across treatment groups using the co-primary ANCOVA model described above. Rubin's rules [Rubin, 1987] will be used to combine results of the imputed datasets using SAS PROC MIANALYZE procedure. As a result, a single estimated treatment difference and its standard error will be produced, with which a 95% CI will be calculated.

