Model Checking & Diagnostics

 • Refer to Appendix 12: Model Checking and Diagnostics for Statistical Analyses.
Model Results Presentation

 • All available observed Hgb values (on and off-treatment) will be summarized using mean, standard deviation, minimum, P25, median, P75 and maximum at each visit by treatment group. In addition to scheduled visits, the baseline value and mean EP and mean Alt EP values will be included (see Section 10.6.3).

Primary Hgb Efficacy Statistical Analyses

- This summary of Hgb will also be repeated for visits up to and including Week 52, using the data used for the primary Hgb analysis (i.e., including imputed values (see Section 10.6.3)).
- All available observed Hgb change from baseline values (on and off-treatment) will also be summarized using mean, standard deviation, minimum, P25, median, P75, and maximum at each post-baseline visit, including mean EP and mean Alt EP values (see Section 10.6.3).
 - This summary of Hgb will also be repeated for visits up to and including Week 52, using the data used for the primary Hgb analysis (i.e., including imputed values (see Section 10.6.3)).

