- The number and percentage of subjects with imputed data in the primary Hgb analysis will be provided by treatment group. The number and percentage of subjects by reason for data imputation will be provided. Reasons include: intermittent missing Hgb values, death before Week 28, death during Week 28 – 52, investigator site closed before Week 28, investigator site closed during Weeks 28-52, lost to follow-up before Week 28, lost to follow-up during Week 28 – 52, consent withdrawn before Week 28, consent withdrawn during Week 28 – 52, and other monotone missing Hgb values. Subjects will be further classified as either having observed all 7 scheduled EP Hgb values, having observed a partial schedule of EP Hgb values, having observed no scheduled EP Hgb values with at least one unscheduled EP Hgb value, or having observed no EP Hgb values, scheduled or unscheduled. For subjects with partial scheduled EP Hgb values, both the pattern of imputed data (intermittent, monotone) and the amount of imputed data (1 – 6 scheduled Hgb values missing) will be summarized. For subjects with partial scheduled EP Hgb values and a monotone imputed data pattern, the reason for the monotone imputed scheduled EP Hgb values will be provided. Reasons include: death during Week 28-52, investigator site closed during Weeks 28-52, lost to follow-up during Week 28 – 52, consent withdrawn during Week 28 – 52, and other monotone imputed Hgb values. And for summaries of the amount of missing scheduled EP Hgb values, the presence or absence of additional unscheduled EP Hgb values will be summarized.
- The least square (LS) mean estimates and standard errors by treatment group, LS mean difference, two-sided 95% CI and one-sided non-inferiority p-value for the difference in the primary Hgb endpoint between the daprodustat and darbepoetin alfa arms from the ANCOVA model will be presented. The number of subjects contributing to the analysis and the associated mean and standard deviation of the baseline and EP Hgb values will also be displayed with the results of the ANCOVA model.
- The LS mean difference, and associated two-sided 95% CI will be displayed on a forest plot together with supportive analysis results (excluding the Tipping Point Analysis).

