- All available Hgb values (on and off-treatment, observed and imputed (see Section 10.6.3)) will be displayed graphically for each scheduled study visit using a line plot. The line plot of mean values \pm 95% CIs by time will include horizontal reference lines to depict the Hgb analysis range (10-11.5 g/dL), vertical reference lines to identify the EP (weeks 28-52), and the number of subjects by treatment group contributing to each mean value.
- All available Hgb change from baseline values (on and off-treatment, observed and imputed (see Section 10.6.3)) will be displayed graphically for each scheduled study visit using a line plot. The line plot of mean values \pm 95% CIs by time will include vertical reference lines to identify the EP (Weeks 28-52), and the number of subjects by treatment group contributing to each mean value.

CONFIDENTIAL

201410

Primary Hgb Efficacy Statistical Analyses

 A listing of all hemoglobin values will be provided, including treatment, most recent dose, site ID, unique subject ID, visit, assessment date, select demographic information and central laboratory and HemoCue Hgb values.
Model Results Interpretation

 Non-inferiority will be achieved if the lower limit of the two-sided 95% CI of the treatment difference is greater than the pre-specified non-inferiority margin of -0.75 g/dL.

Sensitivity Statistical Analyses
Tipping Point (Multiple Imputation) Analysis

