10.6.3. Efficacy

10.6.3.1. Hemoglobin Endpoints

Hemoglobin Values
Central Laboratory and HemoCue Hgb Values

 When source of Hgb measurement is not specified: 
 For reporting purposes, central laboratory Hgb values will be used, unless otherwise specified. However, if a central laboratory Hgb value is missing, a corresponding non-missing HemoCue Hgb value will be used. This approach will be used for the primary Hgb analysis. Some displays may be created for either central laboratory Hgb values only or HemoCue Hgb values only. The central laboratory summary will be considered the primary summary in this case.
Evaluable Hemoglobin Values

 Evaluable Hgb values are on-treatment Hgb values (see Section 10.4.1.1) that are not taken within the 8 weeks following a red blood cell transfusion, a whole blood transfusion, or a non-randomized ESA treatment which occurs on or after the randomization date. Red blood cell transfusions, whole blood transfusions and non-randomized ESA treatments occurring on or after the randomization date are identified by comparing the start and stop date of the respective transfusion or ESA concomitant medication record to the randomization date.
Imputed Hemoglobin Values

 For each missing value between baseline to Week 52 (inclusive), 200 imputed values will be generated using the multiple imputation method (see Section 7.1.2). The average of these 200 imputed values will be used as the value for this missing value in the summary tables and figures. For the primary efficacy Hgb analysis and the corresponding subgroup analyses using all available observed and imputed Hgb values (on and off-treatment), Rubin's rules [Rubin, 1987] will be used to combine results of the imputed datasets using SAS PROC MIANALYZE procedure.
EP Hemoglobin Value for Primary Hgb Analysis

 For each subject, the mean of all available (on and off treatment) Hgb values during the EP (See Section 10.6.1) including any imputed and unscheduled Hgb values that were taken during this time period. Should the assessment dates for Hgb values from the Early Treatment Discontinuation visit fall within the EP, then these values will be included as unscheduled Hgb values. Hgb values from the Follow-up visit will not be included in the EP mean.

CONFIDENTIAL

201410

Hemoglobin Values					

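### By-visit Hgb plots and tables that include imputed data treat the average of 200 imputations as one observed value, so their 95% CIs and SDs are too narrow; the primary inference is unaffected

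*SAP*

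**What the plan says.** SAP 7.1.2.5 creates the imputations "using PROC MI procedure with NIMPUTE = 200 and MCMC IMPUTE = monotone to generate 200 datasets with only monotone missing patterns", followed by a regression step for the monotone gaps. On range it says: "The low and high cutoffs at Hgb values of 6 g/dL and 15 g/dL will be applied to all imputed Hgb values". SAP 10.6.3.1 then sets two rules:

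- **Displays:** "The average of these 200 imputed values will be used as the value for this missing value in the summary tables and figures".
- **Primary analysis and its subgroup analyses:** results from the imputed datasets are combined by Rubin's rules.

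Under Model Results Presentation, SAP 7.1.2.5 applies the display rule in these places:

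- The by-visit tables of Hgb and of change from baseline (mean, SD, quartiles, range, with rows for the EP and alternative EP means) are first produced on observed values, then repeated up to Week 52 "using the data used for the primary Hgb analysis (i.e., including imputed values").
- Two line plots, of Hgb and of change from baseline, use observed plus imputed values. They show by-visit means with intervals; for the Hgb plot, the "95% CIs by time will include horizontal reference lines to depict the Hgb analysis range". Both plots print the number of subjects behind each mean.
- Beside the primary result, "the associated mean and standard deviation of the baseline and EP Hgb values will also be displayed with the results of the ANCOVA model". The SAP does not say how this EP SD is computed when values are imputed.

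No section pools the by-visit SDs or CIs over imputations.

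**The concern.** The average of 200 draws for one subject and visit is close to the conditional mean from the imputation model. It carries neither the residual scatter of a real Hgb value nor the uncertainty of the fitted model. A mean, SD and n computed on a file filled this way treat a prediction as a measurement.

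At stake is how the displays are read. The error bars on the by-visit Hgb curves will be too short wherever data are missing. The repeated tables will tend to show less spread than the observed-only tables next to them, and a reader could take that for a real difference. The printed n will include subjects with no measurement at that visit. The visit means are essentially unaffected.

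**Working it through.** **Planning figures.** Protocol 9.2.1 gives SD 1.5 g/dL, 150 per arm and 30% loss, which leaves 105 per arm. The half-width is t(0.975, 208) × 1.5 × √(2/105) = 0.408, and -0.75 + 0.408 = -0.342. Power by the t test is 95.0%. All agree with Protocol 9.2.1 and 9.2.2. The check below uses SD 1.5 and n = 150 only to express widths in g/dL; the ratios do not depend on the SD.

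**Direction.** The sample variance is convex in the data. The variance of the averaged file therefore cannot exceed the mean W* of the 200 within-dataset variances. Rubin's variance of a mean, T = W + (1 + 1/200)B with W = W*/n, is larger again. So the SD and CI are too narrow whenever values are imputed. For quartiles this is the expected result, not a certainty in every dataset.

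**Size.** Let f be the share missing at a visit and R² the share of variance that the imputation model explains, with data missing completely at random.

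- Variance of averaged-value data: σ²[1 - f(1 - R²)], so SD ratio = √[1 - f(1 - R²)].
- Correct variance of the visit mean: (σ²/n)[R² + (1 - R²)/(1 - f)].
- CI ratio = √{[1 - f(1 - R²)] / [R² + (1 - R²)/(1 - f)]}.
- Coverage = 2Φ(1.96 × CI ratio) - 1.

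Example, f = 0.20 and R² = 0.50: SD ratio = √0.90 = 0.949; CI ratio = √(0.90/1.125) = 0.894; coverage 92.0%. With SD 1.5 and n = 150 the complete-data half-width is 1.96 × 1.5/√150 = 0.240. The averaged-value half-width is 0.240 × 0.949 = 0.228 g/dL and the correct one is 0.240 × √1.125 = 0.255 g/dL.

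| f | R² | SD ratio | CI ratio | Coverage |
|---|---|---|---|---|
| 0.10 | 0.25 | 0.962 | 0.924 | 93.0% |
| 0.10 | 0.75 | 0.987 | 0.974 | 94.4% |
| 0.17 | 0.75 | 0.979 | 0.954 | 93.9% |
| 0.20 | 0.25 | 0.922 | 0.846 | 90.3% |
| 0.20 | 0.50 | 0.949 | 0.894 | 92.0% |
| 0.20 | 0.75 | 0.975 | 0.946 | 93.6% |
| 0.21 | 0.25 | 0.918 | 0.838 | 90.0% |
| 0.30 | 0.25 | 0.880 | 0.766 | 86.7% |
| 0.30 | 0.75 | 0.962 | 0.914 | 92.7% |

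**A rough anchor for f.** Protocol 9.2.1 assumes that "up to approximately 30% of subjects will permanently stop randomized treatment before Week 28". For subjects off treatment, Protocol 5.5.1 has: "Day 1 through Week 52: Study visits every 12 weeks". At that spacing a subject supplies 2 or 3 of the 7 scheduled EP values. Missing share: 30% × 4/7 = 17.1% to 30% × 5/7 = 21.4%, averaged over the EP.

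**Simulation with random missingness** (n = 150, three predictors, 200 imputations, 4,000 replicates, same range of f and R²): CI ratio 0.755-0.973, coverage 86.6-94.5%, interquartile-range ratio 0.80-0.985 (0.928 at f = 0.20, R² = 0.50). Rubin-pooled intervals covered 94.9-95.8%.

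**Simulation with early dropout** (n = 150, 14 four-weekly values, first missed visit at Weeks 4 to 28, sequential regression imputation, 200 imputations, values clipped to 6-15 g/dL, 1,000 runs per setting, two assumed correlation patterns). Ratios at Week 52 against Rubin pooling:

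| Missing | SD ratio | IQR ratio | CI ratio | Coverage, averaged values |
|---|---|---|---|---|
| 10% | 0.95-0.96 | 0.88-0.92 | 0.89-0.91 | 93-94% |
| 20% | 0.89-0.91 | 0.76-0.85 | 0.79-0.83 | 88-92% |
| 30% | 0.83-0.86 | 0.65-0.78 | 0.69-0.74 | 85-86% |

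Rubin-pooled intervals covered 95-96%. The SD and CI were narrower in every run, and the IQR in at least 99.8% of runs. At 30% missing, the half-width was 0.21 g/dL with averaged values against 0.29-0.30 g/dL pooled.

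The narrowing is stronger here because the last observed value lies at least 52 - 24 = 28 weeks before Week 52, so prediction is weak. The closed form at f = 0.20 and R² = 0.10 gives a CI ratio of 0.818, in line with this.

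**The case against.** No decision rests on these displays. They show per-arm means, with no test and no link to the -0.75 g/dL margin. The SAP also gives the reader several safeguards: observed-only tables, a detailed count of subjects with imputed data by reason and pattern, and an imputation-free set of summaries and figures for evaluable Hgb. All of this stands and is why the point is minor. It does not remove the problem. The all-available line plots are planned only with imputed data, and the evaluable-Hgb figures answer a different, on-treatment question.

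The SAP states no CI formula for the plots. That is correct: the finding assumes the usual mean, SD and n of the plotted values. Since SAP 10.6.3.1 supplies one value per subject for figures, this is the natural reading. If pooling is intended, the section needs to say so.

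The size is weakly anchored, and this also stands:

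- The 30% is treatment discontinuation and may already include deaths and withdrawals.
- The 17-21% is an EP average. If off-treatment visits fell at Weeks 28, 40 and 52, these subjects would add no missing values there and 30% at the other four visits. Assignment to a nominal visit depends on eCRF recording (SAP 10.3.1).
- The R² range is not from the documents, and gaps after discontinuation are not completely random.

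These objections bear on the amount of narrowing, not its direction. The early-dropout results suggest the closed-form figures may be too mild.

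**Conclusion.** The concern holds, as a minor point of presentation. Affected are the 95% CIs in the two by-visit line plots, and the SDs, quartiles and range in the repeated tables, including their EP and alternative EP rows. The EP SD shown beside the ANCOVA may be affected; the SAP does not settle it. Not affected are the visit means, the primary estimate with its CI and non-inferiority test, the subgroup and tipping-point results, the observed-only tables and the evaluable-Hgb displays.

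The size is conditional on assumed missingness and R². At 17-21% missing and R² 0.25-0.75, SDs are 2-8% too small, CIs 5-16% too narrow and coverage is 90-94%. Over 10-30% missing and the same R², the figures are 1-12%, 3-23% and 87-94%. Early dropout with weak prediction gives CIs 9-31% too narrow over 10-30% missing. All of this assumes that the plotted CI is computed from the averaged values in the usual way.

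**What to change.** Replace the averaging rule for displays in SAP 10.6.3.1 with wording such as:

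> For by-visit plots that include imputed data, the mean and its variance will be computed in each of the 200 completed datasets and combined by Rubin's rules to give the plotted 95% CI. In tables, the SD will be the square root of the mean within-dataset variance and quartiles will be averaged across datasets; minimum and maximum will be taken from observed values.

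Apply the same rule to the EP and alternative EP rows, and state in SAP 7.1.2.5 that the EP SD beside the ANCOVA is computed this way. The conventions for quartiles and extremes are a choice; another could serve if it is stated and footnoted.

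A simpler alternative for the plots is to show observed data only, with the observed n at each visit.

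The cost is a few sentences and a short macro, since the 200 datasets already exist. The error bars become slightly wider. The estimand, margin and primary test do not change.

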10.1. Appendix 1: Protocol Deviation Management and Definitions for Per Protocol Population

10.1.1. Exclusions from Per Protocol Population

Exclusions from the PP population include events that, if they should occur, might:

- Directly impact the hemoglobin efficacy endpoint; or
- Lead to permanent discontinuation of study treatment or study withdrawal and hence indirectly impact the efficacy endpoint by causing data to be missing.

The following criteria define the events which, if they occur prior to the end of the EP, may lead to exclusion of a subject from the PP population. Exclusions from the PP Population will be subject to blinded review by the study team. The study team will also review the listing of unique concomitant medication terms to identify the prohibited medications. These reviews will occur before database has been unblinded for analysis.

A subject meeting any of the following criteria will be excluded from the Per Protocol population:

Number	Exclusion Description
01	Baseline HemoCue Hgb value outside of Randomization (Day 1) Hgb entry criteria range
02	Less than 5 out of 7 scheduled evaluable ¹ Hgb values ² from the EP
03	Non-compliance with randomized treatment (compliance category of under compliant or over compliant) during the EP, based on eCRF randomized medication exposure and compliance forms
04	Inadequate iron status during EP, defined as ferritin \leq 100 ng/mL on two consecutive scheduled visits or TSAT \leq 20% on two consecutive scheduled visits
05	Subject received prohibited medication ³ for more than two weeks during EP

NOTES:

1. See Section [10.6.3](#).
2. Based on central laboratory Hgb values. If central laboratory Hgb value is missing, a non-missing HemoCue Hgb value will be used.
3. Prohibited medications include strong inhibitors of CYP2C8 (e.g., gemfibrozil) and strong inducers of CYP2C8 (e.g., rifampin/rifampicin).

CONFIDENTIAL

201410

10.2. Appendix 2: Time & Events**10.2.1. Protocol Defined Time & Events****10.2.1.1. Time and Events Table for Subjects on Randomized Treatment**

Protocol Activity (visits \pm 1 week, except Weeks 2 and 4 which are \pm 3 days)	Screening Week -2 ¹	Randomization (Day 1)	Weeks 2, 6	Full study visit Weeks 4, 16, 28, 40	Abbreviated study visit Weeks 8, 12, 20, 24, 32, 36, 44, 48	Week 52	Unscheduled	Follow-up Weeks 56-58
Written informed consent ¹⁹	X							
IRT system	X	X	X	X	X		X	X
Entry criteria	X	X						

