10.3. Appendix 3: Assessment Windows

10.3.1. Assessment Windows

Data for continuous variables that are not related to time-to-event will be summarized according to the scheduled visit time period for which they were recorded in the eCRF. Unscheduled assessments will not be slotted to a particular time point, but will remain as unscheduled if they are either summarized or listed unless otherwise specified (i.e. Hgb endpoints described in Section [10.6.3](#) and BP endpoints described in Section [10.6.4](#)).

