EP Hemoglobin Value for While On-Treatment Evaluable Hgb Supportive Analysis					

 For each subject, the mean of all evaluable Hgb values during the EP (See Section 10.6.1) including any evaluable unscheduled Hgb values that were taken during this time period. Should the assessment dates for Hgb values from the Early Treatment Discontinuation visit fall within the EP, then these values will be included as unscheduled Hgb values. Hgb values from the Follow-up visit will not be included in the EP mean. 					
EP Hemoglobin Value for Alternative EP Supportive Analyses					

 For each subject, the mean of all Hgb values during the Alt. EP (See Section 10.6.1) including any imputed and unscheduled Hgb values that were taken during this time period. This analysis will be conducted using all available (on and off treatment) Hgb values and separately using evaluable Hgb values only. Should the assessment dates for Hgb values from the Early Treatment Discontinuation visit fall within the Alt. EP, then these values will be included as unscheduled Hgb values. Hgb values from the Follow-up visit will not be included in the Alt. EP mean. 					
Use of Unscheduled Hemoglobin Values and Multiple Hgb Values on the Same Date					

 The scenarios outlined below provide guidance on the use of unscheduled Hgb values and multiple Hgb values occurring on the same date. Each row represents a single calendar date. Rows outlining scenarios where there is at least one central lab Hgb and at least one HemoCue Hgb on the same date apply only for the derivation of Hgb values to be used in the primary Hgb analysis, where central lab values are used if they are available and if the central lab value is missing, then a corresponding non-missing HemoCue Hgb value is used. Rows outlining scenarios involving combinations of scheduled and unscheduled Hgb values of the same type apply to all Hgb summaries and analysis. 					
Scheduled Central Lab Hgb Value	Unscheduled Central Lab Hgb Value	Scheduled HemoCue Hgb Value	Unscheduled HemoCue Hgb Value	Value to Use	Type/Label
x				Scheduled central lab Hgb value	Scheduled visit
	x			Unscheduled central lab Hgb value	Unscheduled
		x		Scheduled HemoCue Hgb value	Scheduled visit
		multiple ¹		Average of scheduled HemoCue Hgb values	Scheduled visit
			x	Unscheduled HemoCue Hgb value	Unscheduled

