	multiple			Average of unscheduled central lab Hgb values	Unscheduled
			multiple	Average of unscheduled HemoCue Hgb values	Unscheduled
x	x			Average of central lab Hgb values	Scheduled visit
x		x		Scheduled central lab Hgb value	Scheduled visit
x			x	Scheduled central lab Hgb value	Scheduled visit
	x	x		Unscheduled central lab Hgb value	Unscheduled

CONFIDENTIAL

201410

Hemoglobin Values					
	x		x	Unscheduled central lab Hgb value	Unscheduled
		x	x	Average of HemoCue Hgb values	Scheduled visit
1: The dose adjustment algorithm will require sites to obtain two HemoCue Hgb values at some visits.					
Time In Range					
Time in Range During the EP					

 Number of days that a subject's evaluable Hgb is within the analysis range of 10-11.5 g/dL inclusive during the EP (See Section 10.6.1), including any unscheduled evaluable Hgb values that were taken during this time period. Use of unscheduled Hgb values follows the scenarios for unscheduled and multiple Hgb values. Linear interpolation is used to estimate Hgb between visits, accounting for any intermittent missing values (Rosendaal, 1993). 					
Percent Time in Range During the EP					

 Time in Range During the EP / [Earlier of (Date of the last evaluable Hgb value, Week 52 visit date) – Later of (Date of the first evaluable Hgb value that between Week 16 and Week 52 inclusive, Week 28 visit date)] Note: Percent time in/below/above range during the EP is only defined for subjects with a Treatment Stop Date that is on or after their Week 28 visit date, and have at least two evaluable Hgb values on different days, where at least one evaluable Hgb value is contained within the EP and another evaluable Hgb value occurs within the range of the Week 16 visit through 4 weeks following the Week 52 visit, inclusive. 					

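### In the primary Hgb analysis, a scheduled visit with a HemoCue and a same-day unscheduled central value is labelled unscheduled, so the visit is imputed although Hgb was measured that day

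*SAP*

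**What the plan says.** SAP 10.6.3.1 gives the source rule for the primary Hgb analysis. Central laboratory values are used, and "if a central laboratory Hgb value is missing, a corresponding non-missing HemoCue Hgb value will be used". A table then shows, for each combination of values on one calendar date, which value to use and how to label it. On its scope the SAP says: "Rows outlining scenarios where there is at least one central lab Hgb and at least one HemoCue Hgb on the same date apply only" to the derivation for the primary Hgb analysis.

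The row at issue has an unscheduled central value and a scheduled HemoCue marked. The value to use is the "Unscheduled central lab Hgb value" and the label is *Unscheduled*. The same words occur in other rows; only this one also contains a scheduled measurement. By contrast, a scheduled HemoCue alone is labelled *Scheduled visit*. A scheduled plus an unscheduled HemoCue give the "Average of HemoCue Hgb values", also labelled *Scheduled visit*.

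Three other rules then apply:

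- **Imputation (SAP 7.1.2.5), intermittent gaps:** "Intermittent missing post-baseline scheduled Hgb data in both arms through Week 52 will be imputed using PROC MI procedure". **Monotone gaps:** "the missing scheduled Hgb values through Week 52 will be imputed based on the MAR assumption". Both refer to scheduled values.
- **Visit slotting (SAP 10.3.1):** "Unscheduled assessments will not be slotted to a particular time point", unless otherwise specified. The exception for Hgb points to 10.6.3, whose table keeps this row unscheduled.
- **EP mean (SAP 10.6.3.1):** all available values in the EP are averaged, including imputed and unscheduled ones.

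**The concern.** A scheduled HemoCue by itself fills its visit. Add a central value on the same day, which is the SAP's preferred source, and the visit becomes empty. More information leads to a missing visit, and a model-based value is generated for a day on which Hgb was measured.

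Three things follow for the primary analysis. The subject's EP mean takes in an imputed value it does not need. The subject is counted as having imputed data in the summary that SAP 7.1.2.5 requires. And if the empty slot is the subject's last, the gap is monotone, so the tipping-point analysis shifts it by delta. That analysis leaves intermittent gaps unshifted.

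**Working it through.** **The table.** It has 13 rows, of which eight contain a scheduled value:

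1. scheduled central alone
2. scheduled HemoCue alone
3. several scheduled HemoCue values
4. scheduled and unscheduled central
5. scheduled central and scheduled HemoCue
6. scheduled central and unscheduled HemoCue
7. unscheduled central and scheduled HemoCue
8. scheduled and unscheduled HemoCue

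Seven of the eight are labelled *Scheduled visit*. Only the seventh is labelled *Unscheduled*.

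**From label to imputation.** No single sentence says that this visit is imputed; the step has to be assembled. The imputation acts on missing scheduled values. Unscheduled values are not slotted to a visit. The imputed-data summary in SAP 7.1.2.5 has a class for subjects with no scheduled EP value but at least one unscheduled one, so the two are kept apart. Neither document lets a value labelled *Unscheduled* fill a scheduled slot. The slot is therefore empty and is imputed.

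**Effect on one subject.** SAP 7.1.2.5 counts seven scheduled EP values (Weeks 28, 32, 36, 40, 44, 48 and 52). Take one affected visit and six measured ones.

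- As written: 6 scheduled + 1 unscheduled + 1 imputed = 8 values. Weight of the imputed value = 1/8 = 12.5%.
- With the row labelled *Scheduled visit*: 7 measured, 0 imputed.

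The same seven measurements appear both times, so the change in the subject's EP mean is

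(imputed value − mean of the seven measured values) / 8.

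The documents do not give this gap, so I assume a range:

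- 0.5 g/dL: 0.5/8 = 0.06 g/dL
- 1.0 g/dL: 1.0/8 = 0.13 g/dL
- 1.5 g/dL: 1.5/8 = 0.19 g/dL
- 2.0 g/dL: 2.0/8 = 0.25 g/dL

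**Effect on an arm mean.** Frequency is also not given. Assume that a share f of one arm has one such visit, each with a 1 g/dL gap in the same direction. The shift is f × 1/8:

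- f = 1%: 0.01 × 0.125 = 0.00125 g/dL
- f = 10%: 0.10 × 0.125 = 0.0125 g/dL

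The larger figure is 0.0125/0.75 = 1.7% of the margin. For scale, the half-width in Protocol 9.2.1 reproduces: with 105 per arm and SD 1.5, t(0.975, 208) × 1.5 × √(2/105) = 0.408 g/dL. That figure does not depend on this row.

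**Tipping point.** If only the Week 52 slot is affected, it counts as the first missed visit and is shifted by one delta. The subject's EP mean moves by delta/8, for example 0.125 g/dL for a delta of 1 g/dL, before the cut-offs at 6 and 15 g/dL.

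**How the case could arise.** SAP 10.6.3.1 treats Hgb from an Early Treatment Discontinuation visit within the EP as unscheduled, and Protocol Table 7 collects central Hgb at that visit. It could fall on the date of a scheduled visit at which only the HemoCue was obtained. SAP 8.2.4 also allows laboratory tests at unscheduled or retest visits.

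**The case against.** The best defence is that one principle fits all 13 rows: the label describes the value used. In the seven other rows with a scheduled measurement, the value used is a scheduled one or an average that includes one. Here it is purely unscheduled, so *Unscheduled* is literally accurate and agrees with the default that unscheduled assessments are not slotted.

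That explains the label, but it does not justify the consequence. An accurate description of where a value came from is no reason to impute a visit at which Hgb was measured.

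Other parts of the defence stand:

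- **The central measurement is kept.** It counts in the EP mean, and only the lower-priority HemoCue goes unused. The imputed-data summary also shows whether additional unscheduled EP values exist.
- **The case is narrow.** Protocol Table 6 schedules central Hgb together with HemoCue at every EP visit. The row needs the scheduled central value to be absent and an unscheduled one to be present on the same date. Only Weeks 2 and 6 have HemoCue without central Hgb, and they lie before the EP.
- **Random imputation noise is not the issue.** With 200 imputations pooled, it largely averages out of the point estimate. Only a systematic gap between imputed and measured values would persist.

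A reader might also draw two stronger conclusions that the documents do not support. The first is that the row breaks the SAP's own source rule. That rule prefers a central value when there is one, the table works by calendar date, and a central value exists on this date. Choosing it follows the stated priority.

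The second is that an affected subject could drop out of the per-protocol population under the criterion "Less than 5 out of 7 scheduled evaluable" values. Rows mixing the two sources apply to the primary analysis only, and note 2 to the table in SAP 10.1.1 has its own HemoCue fallback, so the scheduled HemoCue can still count there.

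**Conclusion.** The point holds as a small data-handling inconsistency in the primary Hgb analysis. One row of the same-date table leaves a scheduled visit empty and open to imputation although Hgb was measured that day. For an affected subject with one such EP visit and the rest measured, an imputed value carries 12.5% of the EP mean where none is needed.

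The label is explicit in the table. The imputation is an inference from several sections read together, with nothing in the documents against it. The sizes rest on assumed gaps and frequencies. Within the ranges shown, the effect on the treatment difference is very small, and the case is probably uncommon. Nothing here puts the non-inferiority conclusion in doubt.

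**What to change.** In SAP 10.6.3.1, change the label of the row with an unscheduled central value and a scheduled HemoCue to *Scheduled visit*, so that the same-day central value serves as the value for that visit. Alternatively, add a sentence that a scheduled visit with any Hgb measured on the same date is not imputed. In either case the central value should enter the EP mean once only, as the visit's value.

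The cost is one table cell or one sentence, plus the matching line in the derivation program, settled before unblinding. The choice of central over HemoCue stays as it is. I see no drawback: the change replaces an imputed value with a measured one.
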